## **16.0 Withdrawal of Subjects**

*16.1 Describe circumstances under which you anticipate subjects could be withdrawn from the research without their consent:*

Participants could be withdrawn from the study if they are not showing up for appointments and/or training sessions, are not consuming the provided snacks, or are not completing or complying with all procedures. They also may be withdrawn if they develop an injury or illness that would prevent

them from doing everything that is expected for the study or which might compromise their health.

*16.2 If applicable, describe any procedures for orderly termination (e.g., discontinuation of a study drug or debriefing after a behavioral intervention):*

If a participant is not complying with the study, the PI or study coordinator will first discuss these difficulties with the participant and explain the importance of adhering to the intervention for the purpose of the study. If it is determined that the participant be terminated or discontinued from the study for reasons as described above, the PI will mitigate issues leading to these problems. The participant will be provided any information which is available to them (baseline body composition, fitness testing, resting metabolic rate). It will then be suggested that the study personnel part ways with the participant

*16.3 Describe procedures that you will follow when subjects withdraw from the research, including partial withdrawal from procedures with continued data collection (e.g., participant declines to continue with regular blood draws, but continues with periodic behavioral questionnaires):*

Any participant can discontinue participation at any point without consequence.

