### 2.2 *State the hypotheses to be tested:*

The standard hypercaloric sports performance diet (500 kcal surplus energy, adequate protein and carbohydrate, judicious fat) and resistance training regimen with excess calories from peanut foods or high-carbohydrate snack foods will result in an average weight gain of 1/2 pound/week in both men and women, with the majority of that gain as lean (fat-free mass) mass.

Weight gain will be more efficient when the excess calories are from peanut foods (compared to control, high-carbohydrate foods) which will be better accepted than the control snacks.

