## 5.0 Study Design and Statistical Analysis Plan

**5.1** *Describe the basic study design/approach (e.g., qualitative study using five focus groups of first year students to describe assimilation into the university community; randomized controlled trial of a behavioral change intervention to increase dietary intake of whole grains; pre- post-test evaluation of new pedagogical techniques to improve adult literacy):*

This study is a randomly assigned intervention study that will evaluate the effect of a 10-wk diet and exercise regimen designed to promote healthy weight gain in athletes and military personnel (who desire weight gain). This will include increasing energy intake by 500 additional kcal/day (above weight maintenance diet) through daily provision of either peanut-based whole foods/snacks (peanut group) or a similar, high-carbohydrate, peanut-free snack (control group) along with a supervised resistance training regimen.

*5.2 Describe corresponding data analysis plan/approach (e.g., content analysis of focus group transcripts; descriptive analysis followed by linear regression modeling; nonparametric analysis of pre- and post-test measures):*

Data will be analyzed using IBM SPSS statistics software. Repeated measures ANOVA will be used to assess changes in dependent variables including participant body weight, body composition and anthropometric variables by group and across time (Aim 1). Student t-tests and simple and partial correlation statistics (Pearson Product or Spearman Rank) will be used to evaluate the magnitude of change in body weight/lean mass according to participant characteristics (sex, age, training status, somatotype) and significant adaptive changes in thermogenesis and appetite (Aim 3). Descriptive statistic methodologies will be applied to evaluate the ease and acceptability of peanut foods in the weight gain meal plan (Aim 2). The significance level will be set a priori at  $p < 0.05$

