## 8.0 Procedures Involved

### 8.1 Describe and explain the study design:

Sixteen men and sixteen women between the ages of 18 and 40 will be randomly assigned to the peanut intervention or control group (8 men/8 women/group). A computer program with a random number generator will be used by the study coordinator to assign male participants and female participants to the peanut or control group (i.e., each sex will be separately randomized).

As outlined in the table, eligible participants will undergo a 10-wk diet and training regimen designed to promote healthy weight gain. This will include increasing energy intake by 500 additional kcal/day (above their typical weight maintenance diet and accounting for energy requirements of resistance training) through provision of peanut-based whole foods/snacks or high-carbohydrate containing control snacks along

with a supervised rigorous resistance training regimen designed to promote muscle hypertrophy. After providing informed consent, participants will be randomly assigned to the peanut or control group based on sex. Outcome data will include assessment of body mass, total and regional body composition via DXA and body anthropometrics, skinfolds and somatotyping using the International Standards for Anthropometric Assessment (ISAK) (Stewart, Marfell-Jones et al. 2011) along with measures of resting metabolic rate (RMR), circulating hormones and serum/plasma biomarkers. The latter includes measurement of potentially important hormones/ biomarkers of anabolism, stress, overfeeding, and cardiometabolic health. Compliance to the nutrition and exercise regimen will be evaluated at regular intervals and include collection of 3-day food records (performed at baseline and 3-days prior to each assessment point) and physical activity data collected by digital technology (Garmin Vena SQ smart watch and My PT Hub app).

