## 14.0 Number of Subjects

14.1 *Indicate the total number of subjects to be enrolled and how this number was determined (e.g., sample size calculation [show], number of available subjects in a finite pool, number of tests funding award would allow):*

The sample target of 16 men and 16 women was selected because we believed it would be feasible to recruit and study this number within the time frame and budget set by the funding agency. We, however, will target recruitment of up to 40 participants. Based on limited previous studies in men who have used a range of 12 to 46 subjects, we also believe this number is sufficient to show measurable results.

14.2 *If this is a multi-site study, indicate the number of subjects to be enrolled at this site and the total to be enrolled from all sites:*

N/A

*14.3 If applicable, indicate the number of potential subjects you expect to screen for enrollment, and the number of subjects you will need to complete the research procedures:*

We anticipate that we may need to screen between 100 and 150 participants to recruit and complete the required 32 participants.

*14.4 If the study has more than one procedure, indicate the total number of subjects to undergo each procedure separately:*

20 participants (~10 men/10 women) will be assigned to the peanut-containing snack group and 20 participants (~10 men/10 women) will be assigned to the control snack group as previously mentioned.

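### Staff may withdraw randomised participants from the study for not eating the assigned snacks or missing sessions, with no later follow-up planned, so the week-11 comparison may rest mainly on adherers

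*Combined protocol and SAP*

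**What the plan says.** Section 16.1, on involuntary withdrawal, states: "Participants could be withdrawn from the study if they are not showing up for appointments and/or training sessions, are not consuming the provided snacks". The withdrawal is from the study, not only from the snacks or the training. No level of attendance or consumption is given as the trigger.

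Section 16.2 requires a conversation before that step: "the PI or study coordinator will first discuss these difficulties with the participant". If it fails, "It will then be suggested that the study personnel part ways with the participant". The template prompt for section 16.3 asks about partial withdrawal with continued data collection. The whole answer is: "Any participant can discontinue participation at any point without consequence".

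These withdrawals come after randomisation, because section 8.1 says: "After providing informed consent, participants will be randomly assigned to the peanut or control group based on sex". The study coordinator makes the assignment (8.1), can open the file holding the randomisation order (9.4), and is one of the two people named for the non-compliance discussion (16.2).

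On numbers, section 14.3 says: "We anticipate that we may need to screen between 100 and 150 participants to recruit and complete the required 32 participants". Section 14.1 sets a recruitment ceiling of 40, and the revision history (revision 6) explains the increase as cover for drop-outs so that 32 complete. On analysis, section 5.2 says: "Repeated measures ANOVA will be used to assess changes in dependent variables including participant body weight". It states no analysis population and no handling of missing visits.

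Section 2.2 predicts that weight gain will be more efficient with the peanut foods, "which will be better accepted than the control snacks". The snack rating is listed among the primary endpoints in section 4.1. Table 1 and the week-11 session in section 8.2 schedule it once, at week 11.

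**The concern.** Whether someone keeps eating the snack can be a consequence of the arm they were given. Removing people on that basis is selection after randomisation on something the arm can affect, so the two groups left at week 11 need no longer be comparable. With no threshold and with staff who can know the arm, removal decisions can also differ between arms for reasons unrelated to behaviour.

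Three results are exposed:

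- The between-arm comparison of weight and lean mass can be biased.
- The mean gain set against the hypothesised 1/2 lb per week can be raised, because people who stop the regimen are not counted.
- The acceptability rating will be missing for those who found the snacks least acceptable. This loss follows from the visit schedule and does not depend on how the ANOVA is run.

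**Working it through.** **The plan's own figures.** No power calculation is given, since section 14.1 justifies the sample by feasibility and by the size of earlier studies. The only step that can be checked is 32 to 40. With N/(1 − d) and d = 0.20, 32/0.80 = 40. The rate d is not stated, but the ceiling leaves room to lose 40 − 32 = 8 people, or 20%.

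**Inputs for the illustration**
- From the plan: 20 per arm (14.4); a gain of 0.5 lb/week × 10 weeks = 5 lb (2.2).
- Assumed: all 8 losses are staff withdrawals for not eating the snacks; adherers gain 5 lb in both arms; non-consumers gain g lb, with g from 0 to 3.

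**Difference hidden by the withdrawals.** Let pP and pC be the fractions withdrawn from peanut and control. The all-randomised difference (peanut minus control) is

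[(1 − pP)·5 + pP·g] − [(1 − pC)·5 + pC·g] = (pC − pP)(5 − g).

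Among those kept it is 5 − 5 = 0.

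| Withdrawn, peanut / control | pC − pP | g = 0 | g = 1 | g = 3 | Among those kept |
|---|---|---|---|---|---|
| 2 / 6 | 0.20 | +1.0 lb | +0.8 lb | +0.4 lb | 0 |
| 4 / 4 | 0 | 0 | 0 | 0 | 0 |
| 6 / 2 | −0.20 | −1.0 lb | −0.8 lb | −0.4 lb | 0 |

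For the 2/6 split with g = 1, the arm means are 0.9 × 5 + 0.1 × 1 = 4.6 lb and 0.7 × 5 + 0.3 × 1 = 3.8 lb.

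**Overall mean gain.** With 20% withdrawn in total, the all-randomised mean is 0.8 × 5 + 0.2 × g. That is 4.0 lb at g = 0, 4.2 lb at g = 1 and 4.6 lb at g = 3, or 0.40 to 0.46 lb/week. Those kept average 0.50 lb/week. The 0.50 is an input and not a finding; the point is the gap of 0.04 to 0.10 lb/week. It remains even when withdrawals are equal between arms.

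**When adherence is only correlated with gain.** Suppose there is no true difference, adherence and gain have correlation r, and the least adherent fraction p of an arm is removed. The mean of those kept rises by SD·r·φ(z_p)/(1 − p), where z_p is the normal quantile at p. The factor φ(z_p)/(1 − p) is 0.1755/0.9 = 0.195 at p = 0.10 and 0.3477/0.7 = 0.497 at p = 0.30, a difference of 0.302. With assumed SD 3 lb and r = 0.3, the bias is 3 × 0.3 × 0.302 = 0.27 lb. With SD 4 lb and r = 0.5, it is 4 × 0.5 × 0.302 = 0.60 lb. It flatters the arm with more removals. In simulation (20 randomised per arm, 20,000 trials), a nominal 5% t-test rejected in about 6% to 8% of trials with 10% against 30% removed, and in about 5% to 6% with 20% removed from each arm.

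**Acceptability.** Under the 2/6 split, 20 − 2 = 18 peanut and 20 − 6 = 14 control participants would supply a rating, and each missing rating would belong to someone who did not eat the snacks.

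**The case against.** The strongest reply is that section 16.1 is a permission and not an analysis rule. Participants could be withdrawn; nothing says that they must be. A discussion comes first, compliance is assessed weekly, and both groups choose among several snacks (8.2), all of which should make removal less frequent. The end-of-study payment requires at least 85% of sessions (15.4), which suggests that some absence is tolerated. Weight and DXA are also taken at weeks 3 and 7, so a late withdrawal leaves some outcome data. All of this stands. A reader might infer that the plan keeps only adherers, or that it prescribes a completers-only analysis. The documents say neither. The completer framing is an inference from the target of 32, the end of contact, and an ANOVA which in its usual form drops incomplete cases.

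A second reply is that the stated aim is efficacy, and that the section 2.2 hypothesis can be read as gain once the calories are eaten, with acceptability as a separate, descriptive aim. That reading is open. It does not rescue the rule: discretionary removal without a threshold, by staff who can know the arm, gives no unbiased answer to an adherence-conditional question either, because those who keep eating in one arm need not resemble those who do so in the other.

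A third reply is that the figures follow from their assumptions. That is correct. The 8 losses could be voluntary or due to injury or illness, and the split is invented.

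**Conclusion.** The point stands in a limited form. Nothing elsewhere in the protocol provides for week-11 measurement of withdrawn participants or for an analysis of everyone randomised. The comparison may therefore be made mainly in adherers, and it can be biased.

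The size and direction of that bias are unknown. A reader might infer from section 2.2 that removals will fall on the control arm and so work against peanuts. That prediction is an untested hypothesis, and the documents give no withdrawal rates by arm. The 0.4 to 1.0 lb, against a planned gain of 5 lb, holds only for a 2/6 or 6/2 split, equal gains among adherers, and non-consumers gaining 0 to 3 lb. With equal withdrawal the between-arm bias is zero in this illustration.

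Two consequences need no assumption about the split. The mean gain is raised whenever those removed gain less than those kept. The week-11 acceptability rating is also lost from people withdrawn for refusing the snacks. This is a cheap improvement to make before the data are collected, since measurements not taken cannot be recovered at analysis.

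**What to change.** Leave the criteria for stopping the snacks or training as the sponsor decides, and leave withdrawal for injury, illness or pregnancy as it is. Change only follow-up and analysis.

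- **Sections 16.1 to 16.3.** State that stopping the snacks or training is not the same as leaving the study. With consent, and where the measurement is safe, a participant who stops is still invited to the remaining scheduled weight and DXA measurements and to the week-11 snack questionnaire. Align the consent form.
- **Section 5.2.** Base the main comparison on all randomised participants by assigned arm, using every available visit, for example with a mixed model with arm, visit and their interaction. Give the adherers-only result as a sensitivity analysis, and define adherence for that purpose in advance.
- **Reporting.** Give withdrawals and their reasons by arm, separating staff decisions from voluntary ones.

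The cost is protocol and consent wording and a few visits that are already in the schedule. Section 15.4 lists no payment for the final visit apart from the attendance condition, so the sponsor should settle how those who stopped are treated. The mean gain will be somewhat diluted. A mixed model still relies on a missing-at-random assumption for people who decline further visits, which is why the visits themselves matter most.

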## 17.0 Risks to Subjects

*17.1 List the reasonably foreseeable risks, discomforts, hazards, or inconveniences to the subjects related to the subjects' participation in the research. Include for the IRB's consideration a description of the probability, magnitude, duration, and reversibility of the risks. Consider physical, psychological, social, legal, privacy, and economic risks. Do not indicate "No risk" or "N/A." Instead, for studies with very low risk (e.g., anonymous online questionnaire on a mundane topic) indicate "The investigators are not aware of any risks from participation in this study." or "No more than risks than are found in everyday life." The example consent form presents a tabular method for risk information, which you can also use here. Common risk types include:*

- *Physical (e.g., potential for pain, discomfort, infection)*
- *Psychological (e.g., potential for stress, discomfort, and/or embarrassment)*
- *Social (e.g., potential for discrimination or stigmatization and disruption of personal and family relationships)*
- *Legal (e.g., potential for disclosure of illegal activity, negligence)*

- *Privacy (e.g., potential for personal information being accessed, used, or disclosed without the subjects' knowledge or consent, breach of confidentiality/security)*
- *Economic (e.g., potential for individuals to lose access to economic services, employment, insurability)*

Resting Metabolic Rate: Risk of claustrophobia or feelings of anxiety during testing when the clear ventilated hood is placed over their head. To minimize this risk, participants will be screened for claustrophobia and monitored for signs and symptoms that can include sweating, shakiness, tachycardia, increased or rapid breathing, nausea, light-headedness, fainting and fear of actual imminent physical harm. An investigator will monitor this test to ensure participant safety.

DXA Scan: The amount of radiation that subjects will receive in the DXA exam is less than the amount permitted by the Food and Drug Administration (FDA) per year. The amount subjects will receive at each scan is equal to 1/20 of a chest x-ray. The more radiation an individual receives over the course of their lifetime, the more likely that individual's risk increases in developing cancerous tumors. The radiation in this study is not expected to greatly increase these risks, however, the exact increase in such risk is not known.

Blood draws: Slight discomfort may be expected during blood draws. Risk of developing a small bruise or blood clot in the vein, risk of fainting or dizziness, risk of infection and risk of bleeding are also possible. Universal Precautions will be followed for collection, handling, processing, and disposal of items that may have come into contact with bodily fluids during the collection of blood. Blood draws will be performed by a research phlebotomist ([name]) trained and experienced in the blood draw procedure and in handling minor emergencies such as dizziness and fainting. In case of an emergency, 911 will be called.

Walking Economy and Exercise Capacity (VO2max): There is a small risk of orthopedic injury, treadmill falls or cardiovascular complications that could require a participant to go to the hospital. This includes a heart attack, or even death. In studies involving people with heart disease, the risk of hospitalization was 1 in 500 tests (<0.20%). The risk of heart attack was 1 in 2,500 tests (0.04%) and death, 1 in 10,000 tests (0.01%). The risks are likely to be lower in young, healthy subjects who are involved in athletic training and/or exercise. Only experienced staff members will conduct these tests and subjects will be monitored throughout the test for signs of problems based on standards of the American College of Sports Medicine (ACSM). There is a possibility some subjects will be tired after this test and could have sore muscles for a few days.

24-hour urine collection: There are no risks for urine collections. However, 24-hour urine collections may present some inconvenience and/or embarrassment. The inconvenience will be minimized by the provision of a reusable shopping bag to make carrying and storage discrete. Also, female participants will be provided with a female urination devise to make this collection easier.

Continuous Glucose Monitoring. The placement of the device will require that a sensor is inserted into the back of the participant's upper arm. Placement of the sensor may induce some pain during the insertion, inflammation, redness, swelling, minor bleeding and/or minor infection at the site. This will all be minimized by having a trained individual perform the procedure which will take place in aseptic conditions. There is also a possibility a participant may experience these symptoms as a result of contact between the adhesive pad of the sensor and the skin; allergic reactions can also develop in response to the adhesive used to keep the device in place. If any of these symptoms occur, the participant will be informed that he/she has the ability to remove the CGM and these issues will clear up within a short time period.

Dietary Intervention: There are no real risk to consuming the intervention snacks. The peanut group will be provided with a variety of whole and laboratory-prepared peanut-containing snacks to meet their daily excess energy target of ~500 kcal whereas the control group will be provided a variety of high-carbohydrate snacks. There is a very small chance a participant might develop an allergy or intolerance to one of the snacks. To help avoid this issue, we will screen for a history of food allergies and intolerances including allergies to legumes, peanuts and tree nuts, as well as eggs, dairy, gluten and fermentable carbohydrates.

Resistance (Weight) Training: This project will use standard resistance training procedures with Nautilus equipment that follows ACSM and IUSCA guidelines. Major health organizations recommend resistance training for all age groups, and have found it to be safe with low risk of injury. The most likely possible risk includes muscle soreness. Other possible risks include muscle or joint injury or an abrupt elevation of blood pressure. Our program will recruit only participants who have previous experience with resistance training. The resistance training sessions will be supervised by ACSM-certified personal trainers and emphasize proper form, lifting procedures, and breathing techniques. The program will also be tapered upward over the first ~2 weeks to help prevent excessive muscle soreness and muscle or joint strain. Increases in blood pressure are also unlikely in the population studied. The participants will be informed to contact the PI or any member of the research team in the case of any injury or excessive joint or muscle strain.

*17.2 Indicate the measures you will use to minimize risks and monitor subjects for safety. (e.g., asking a subject at regular intervals to rate how they are feeling from 1 to 10, or to slowly crouch in order to check their balance.)*  
*Indicate the measures you will use to minimize risks and monitor subjects for safety. (e.g., asking a subject at regular intervals to rate how they are feeling from 1 to 10, or to slowly crouch in order to check their balance.)*

Included in Section 17.1

*17.3 If applicable, indicate which procedures might have risks to the subjects that are currently unforeseeable. This will be rare, and usually applicable when testing a new drug or device or a new use of an existing drug or device:*

It is possible that participants could develop severe muscle soreness by participating in our rigorous resistance training regimen. It is also possible an unknown allergy to peanuts could be identified during the study. These events, however, are not likely. To minimize the potential, we will slowly increase the resistance (weight) used during training over the first 2 weeks and are also recruiting participants who have some previous history of strength/resistance training. A previously known allergy to legumes, nuts or tree nuts is an exclusion criterion for the study.

*17.4 If applicable, indicate which procedures might have risks to an embryo or fetus should the subject be or become pregnant:*

There is minimal risk if a female participant were to become pregnant during the 10 weeks of the study. The most recent committee opinion of the American College of Obstetricians and Gynecologists (April 2020) states that physical activity and exercise (including resistance exercise) in pregnancy are associated with minimal risks and have been shown to benefit most women. Pregnancy tests will be performed at four timepoints during the study (specifically before each DXA), to ensure the participant is not pregnant. Participation in the study would end if it were determined the participant had become pregnant.

*17.5 If applicable, describe risks to others who are not subjects (e.g., collection of sensitive health data that might affect sexual partners if disclosed, mandatory reporting of abuse, DNA testing that might affect family members or relationships):*

N/A

